Two subsets of patients who agree to participate at specific investigational centers and to wear an accelerometer either on the ankle to measure TDS (n=100) or on the wrist to measure SDI (n=100) will be instructed on the proper use of these devices at the baseline visit (visit 2). The devices will be worn throughout the 12-week intervention period and will be returned to the investigational center at the final visit or upon early termination.

Brief Summary of Study Design for the Trial Registry:

This is a 12-week, multicenter, open-label study to evaluate the relationship between ABS eMDPI and CE-COPD in adult patients at least 40 years of age with exacerbation-prone COPD. The ABS eMDPI dose will be 90 mcg, 1 to 2 inhalations every 4 hours as needed, but patient dosing will not be limited to this dosing regimen. The purpose of this study is to evaluate the relationship between albuterol dosing and CE-COPD.

Method of Randomization and Blinding: This is a nonrandomized study. All patients will use the one Test IMP, the ABS eMDPI. Blinding is not applicable.

Investigational Medicinal Products: Dose, Pharmaceutical Form, Route of Administration, and Administration Rate

Test IMP: The ABS eMDPI dose will be 90 mcg, 1 to 2 inhalations every 4 hours as needed.

Reference IMP: Not applicable

Placebo IMP: Not applicable

Duration of Patient Participation and Maximal Exposure to IMP: The total duration of patient participation in the study is planned to be up to 14 weeks (a screening period of up to 2 weeks and a 12-week intervention period).

Study Duration: Approximately 9 months

End of Study: End of study is defined as the last visit of the last patient.

Plans for Treatment or Care After the Patient Has Ended Participation in the Study: No treatment is planned by the sponsor after the end of the study. Patients should be treated with standard of care after withdrawal from or termination of the study, as appropriate.

Inclusion Criteria: Patients may be enrolled in the study only if they meet all of the following criteria:

- a. The patient is male or female, 40 years of age or older, with a physician diagnosis of COPD. The diagnosis should include a history of forced expiratory volume in 1 second (FEV₁)/forced vital capacity <70% predicted and FEV₁ <80% predicted documented in the patient's chart.

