4.3. Withdrawal Criteria and Procedures for the Patient

Each patient is free to withdraw from the study at any time, without prejudice to their continued care. Patients must be withdrawn from the study if any of the following events occur:

- a. Patient withdraws consent or requests discontinuation from the study for any reason.
- b. Patient develops an illness that would interfere with his/her continued participation.
- c. Patient is noncompliant with the study procedures and assessments or administration of ABS eMDPI, in the opinion of the investigator.
- d. Patient takes prohibited concomitant medications as defined in this protocol.
- e. A female patient has a confirmation of pregnancy during the study from a positive pregnancy test.

- f. The sponsor requests withdrawal of the patient.
- g. Patient experiences an adverse event or other medical condition that indicates to the investigator that continued participation is not in the best interest of the patient.

Patients should be treated with standard of care after withdrawal from or termination of the study, as appropriate.

Investigators should attempt to obtain information on patients in the case of withdrawal or discontinuation. Results of any evaluations and observations, together with a narrative describing the reason(s) for withdrawal, must be recorded in the source documents. The electronic case report form (eCRF) must document the primary reason for withdrawal or discontinuation.

See [Appendix F](#) for information regarding how the study will define and address patients who are lost to follow-up to help limit the amount and impact of missing data.

If the reason for withdrawal is an adverse event, monitoring will be continued as applicable (eg, until the event has resolved or stabilized, until the patient is referred to the care of a healthcare professional, or until a determination of a cause unrelated to the IMP or study procedure is made). The specific event or test result (including repeated test results, as applicable) must be recorded both on the source documentation and in the eCRF; both the adverse events eCRF and termination eCRF will be completed at that time.

All assessments should be performed according to the protocol for the final visit or early termination (visit 5) if possible. Patients are required to return the ABS eMDPI (used and unused) upon withdrawal from the study.

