5.1.1.1. Starting Dose and Dose Levels

The prescribed dose will be 90 mcg, 1 to 2 inhalations every 4 hours as needed. No dose escalations are planned.

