6.1.2. Albuterol Use

Albuterol usage data will be downloaded using extraction software directly from eMDPI devices collected from the patients at their final study visit after return of the device to the depot.

For albuterol use, parameters of interest will include (1) the total number of inhalations in the days preceding the peak of a CE-COPD, (2) the number of days prior to the peak of a CE-COPD when albuterol use increased, and (3) the number of albuterol uses in the 24 hours preceding a CE-COPD.

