7.3. Medication Error and Special Situations Related to the Investigational Medicinal Products

Any administration of IMP that is not in accordance with the study protocol should be reported either as a violation, if it meets the violation criteria specified in the protocol (Appendix C), or as a deviation, in the patient's source documents, regardless of whether or not an adverse event occurs as a result. When meeting protocol violation criteria, all instances of incorrect IMP administration should be categorized as "Non-Compliance to investigational medicinal product (IMP)."

The following are types of medication errors and special situations:

1. Medication error: Any unintentional error in the prescribing, dispensing, or administration of a medicinal product while in the control of the healthcare professional, patient, or consumer.
2. Overdose: Administration of a quantity of a medicinal product given per administration or cumulatively which is above the maximum recommended dose according to the authorized product information. Clinical judgment should always be applied. Any dose of IMP (whether the test IMP, reference IMP, or placebo IMP), whether taken intentionally or unintentionally, in excess of that prescribed must be immediately reported to the sponsor.
3. Misuse: Situations where the IMP is intentionally and inappropriately used not in accordance with the authorized product information.
4. Abuse: Persistent or sporadic, intentional excessive use of IMP which is accompanied by harmful physical or psychological effects.
5. Off-label use: Situations where an IMP is intentionally used for a medical purpose not in accordance with the authorized product information.
6. Occupational exposure: Exposure to an IMP, as a result of one's professional or non-professional occupation.
7. Breastfeeding: Suspected adverse reactions which occur in infants following exposure to a medicinal product from breast milk.

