5.9. Study Protocol Violations

Any deviation from the protocol that affects, to a significant degree, (a) the safety, physical, or mental integrity of the patients in the study and/or (b) the scientific value of the study will be considered a protocol violation. Protocol violations include non-adherence on the part of the patient, the investigator, or the sponsor to protocol-specific inclusion/exclusion criteria, primary outcome measure criteria, or good clinical practice (GCP) guidelines; noncompliance to study drug administration; use of prohibited medications; or any other deviations that may have an impact on the processes put in place for the care and safety of the patients.

Protocol violations recorded in the Clinical Trial Management System during the study will be summarized overall and for each of the following categories using descriptive statistics:

- Informed Consent Procedures

- Inclusion/Exclusion Criteria
- Concomitant Medications/Therapy
- Lab Assessments/Procedures
- Study Procedures
- Serious Adverse Events
- Randomization Procedures/Dosing
- Visit Schedule/Interval

Of note, any recorded ‘Randomization Procedures/Dosing’ violations related to medication errors, overdose, misuse, abuse, off-label use and occupational exposure will be summarized in the sub-category ‘Non-compliance to study medication’.

Patients with at least 1 protocol violation will be summarized by the above categories (sub-categories) using count and percentages, by analysis set (ITT analysis set, and the ankle and wrist accelerometry analysis sets).

5.10. eMDPI Time on Study; Days and Weeks

Summary statistics of the eMDPI time on study in days and weeks (days divided by 7) will be presented overall and by CE-COPD status and by CE-COPD severity (Yes: severe, moderate; No) for the ITT analysis set, ankle accelerometry analysis set and the wrist accelerometry analysis set.

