7.5.2.2. Time to Clinical (COPD) Exacerbations Short-term Exacerbation Risk (7 days)

For each patient, the following 3 landmark use events will be identified:

- first time in study when had >4 inhalations per day ("low use group")
- first time in study when had >8 inhalations per day ("medium use group")
- first time in study when had >12 inhalations per day ("high use group")

A patient may be included in more than 1 landmark use group (for example, if had >12 inhalations a day any time during study, then on that time or already before he/she also had >8 and >4 a day).

For each landmark use groups, time to CE-COPD within 7 days since the landmark event will be estimated and plotted using Kaplan-Meier plot. The 3 groups will be presented in the same plot, to assess a possible 'dose-response' association, if higher use is associated with shorter time to CE-COPD.

If a CE-COPD has not occurred within 7 days, then that observation will be censored at 7 days or earlier if follow-up had completed/terminated before 7 days elapsed. Note, if CE-COPD occurred on the same date where landmark use happened, then time to CE-COPD will be calculated as 0.

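### The status of albuterol use above the prescribed regimen is contradictory across the protocol, and the only output fed by overdose reports is likely to undercount it

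*Protocol*

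**What the plan says.** **Dose.** Protocol 5.1.1.1 states: "The prescribed dose will be 90 mcg, 1 to 2 inhalations every 4 hours as needed. No dose escalations are planned". Table 2 and SAP 2.1.1.3 agree. The synopsis, in its summary for the trial registry, gives the same regimen and continues "but patient dosing will not be limited to this dosing regimen". Section 5.3.1 cites product information with a 4-to-6-hour interval and advice against more frequent or larger use.

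**Reporting.** Section 7.3 defines overdose against the authorized product information, adds "Clinical judgment should always be applied", and then requires that any dose "in excess of that prescribed must be immediately reported to the sponsor". It also has off-protocol administration reported as a violation if it meets the violation criteria, and otherwise as a deviation in source documents.

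**Withdrawal.** Section 4.3 lists the events for which a patient has to leave the study. Item c is: "Patient is noncompliant with the study procedures and assessments or administration of ABS eMDPI, in the opinion of the investigator".

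**Reading the device.** Section 6.1.2 says: "Albuterol usage data will be downloaded using extraction software directly from eMDPI devices collected from the patients at their final study visit", after the device has gone back to the depot. Appendix B also has devices collected at the exacerbation visit.

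**Analysis.** SAP 7.5.2.2 defines its high-use landmark as "first time in study when had >12 inhalations per day". SAP 5.9 summarises violations logged in the trial management system; those "related to medication errors, overdose, misuse, abuse, off-label use and occupational exposure will be summarized in the sub-category" for non-compliance to study medication. SAP 7.1.2.5 and 10.2 separately summarise device-based maxima.

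**The concern.** The study's hypothesis is that use rises in the days before an exacerbation. The behaviour it sets out to observe is therefore also, on other pages, reportable excess dosing and possible noncompliance. A site that learns of 13 inhalations in a day cannot tell from the protocol whether this is permitted, a deviation, an overdose or grounds for withdrawal.

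Two things are at stake. First, if sites resolve the ambiguity differently, some may withdraw high users before their exacerbation is observed. That loss would be related to both predictor and outcome, and would fall on the patients who are most informative for the hypothesis. Second, safety of eMDPI use is a stated objective. A report could show days above 1080 mcg in its exposure table beside few or no logged overdoses, with nothing to explain the difference and nothing that ties excess days to adverse events.

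**Working it through.** The plan states no figure for excess use, so there is none to reproduce. The check is arithmetic on the regimen and visit windows, then a side-by-side reading.

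**1. Ceiling of the prescribed regimen** (Protocol 5.1.1.1: up to 2 inhalations of 90 mcg every 4 hours).
- 2 × 24/4 = 12 inhalations per 24 hours; 12 × 90 = 1080 mcg.
- At the 6-hour end of the interval cited in 5.3.1: 2 × 24/6 = 8 inhalations; 8 × 90 = 720 mcg.

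The reference for the overdose definition (product information) and for the reporting duty (prescribed dose) are therefore not necessarily the same. Three inhalations within 4 hours also exceed the prescribed regimen at a lower daily total.

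**2. Overlap with the planned analysis.** The SAP 7.5.2.2 high-use group is above 12 a day, so by construction all its members exceed the prescribed regimen.

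**3. Status of use above the regimen, passage by passage.**
- Synopsis: the regimen is not a limit.
- 5.1.1.1, Table 2, SAP 2.1.1.3: the regimen is the prescription.
- 7.3: immediate report, and a deviation or violation.
- 4.3c: withdrawal if the investigator judges the patient noncompliant.
- 5.7: investigator and sponsor together decide on withdrawal.
- Appendix C: the sponsor decides after a reported violation.
- SAP 7.5.2.2: a planned landmark event.

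**4. When excess use can be seen.** Visit 5 is at day 84 ± 14, so a device kept until then is collected between day 70 and day 98, and downloaded later still. For a patient with an exacerbation, Appendix B allows collection within 14 days of its start. The longest gaps between scheduled contacts are:
- day 1 to visit 3: 35 − 1 = 34 days;
- visit 3 to visit 4: 63 − 21 = 42 days;
- visit 4 to visit 5: 98 − 49 = 49 days.

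**5. What the dose counter can show.** It is cumulative. Assume 4 inhalations a day with one day of 14: 27 × 4 + 14 = 122 over 28 days, against 28 × 4 = 112 without the peak and 28 × 12 = 336 at the ceiling. A single-day peak is not visible in the total.

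**6. What reaches the tables.** SAP 5.9 takes logged violations only. Excess use that nobody noticed is not logged, and excess use recorded as a deviation stays in source documents. SAP 7.1.2.5 and 10.2 use device records, so the two sources can disagree.

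**7. Size of the undercount.** The documents give no frequency of use above 12 a day. As an illustration on assumed values only: if 5% to 30% of 400 patients (20 to 120) ever exceed 12 a day, and 0% to 50% of these are noticed and logged as violations, the sub-category would hold 0 to 60 of them.

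**The case against.** The strongest reply is that several safeguards exist.

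- **Detection.** A reader might infer that the overdose report cannot be made at all. The documents do not support that. There are compliance checks at the monthly calls (5.7), adverse-event questions at each contact (7.1.2), a dose counter (5.1.1), site visits for further devices (3.1) and device collection at the exacerbation visit (Appendix B). Section 7.3 also does not say that the duty runs from the dose rather than from awareness. This stands: reporting will be late and incomplete, not impossible.
- **Output.** A reader might infer that an overdose table will be wrong. No such table is planned. Overdose is pooled with five other types, and the sub-category does not claim to count every excess day.
- **Withdrawal.** It rests on judgment in 4.3c, 5.7 and Appendix C. This stands, but judgment exercised against contradictory text will vary by site. Likewise, "Clinical judgment should always be applied" in 7.3 qualifies the overdose definition, while the sentence after it is categorical.
- **Existing device summaries.** SAP 10.2 already gives the maximum exposure in a single day, 7.1.2.5 the maximum in 24 hours, and 7.5.2.1 the days above 12 in the two weeks before an exacerbation. The size of the 7.5.2.2 landmark group would imply how many patients ever exceeded 12. This narrows the gap to patient-days over the whole study and the link to adverse events.
- **Harm.** A reader might cite the drug-related serious tachyarrhythmia in Protocol 1.2.2 as evidence on over-use. That study dosed 2 inhalations twice daily, or 4 a day, so it is not.

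**Conclusion.** The contradiction is in the text and should be resolved. The synopsis does not limit dosing to the regimen; 5.1.1.1, Table 2 and SAP 2.1.1.3 prescribe it; 7.3 makes any excess reportable; and 4.3c allows withdrawal for noncompliance. The 12-a-day ceiling, and hence the complete overlap with the SAP high-use group, follow from the documents' own figures.

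Two consequences are likely but not quantified: uneven handling of high users across sites, and undercounting of excess use in the SAP 5.9 sub-category relative to the device-based maxima. The 0-to-60 illustration rests wholly on assumed frequencies. The cited reliever study used thresholds of more than 10 and more than 20 inhalations a day, which makes such use plausible here but gives no rate for this trial.

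It would go too far to conclude that withdrawal of high users is mandatory or that the safety reporting is invalid. Withdrawal is discretionary, and the device records needed for a fuller account are already being collected.

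**What to change.** 1. Reconcile the synopsis sentence with Sections 4.3c, 5.1.1.1, 5.3.1 and 7.3, so that use above the prescribed regimen has the same status throughout: permitted, deviation, overdose or grounds for withdrawal. Which of these applies is the sponsor's decision.

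2. In SAP 10.2, beside the existing maximum daily exposure, add from the eMDPI download the number of patients and patient-days above the prescribed regimen as reconciled. The SAP's own category of more than 12 a day is one possible definition. Show adverse events that start on those days or the next.

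3. State in SAP 5.9 that the non-compliance sub-category covers logged violations only.

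The cost is protocol wording, one more table from data already collected and one SAP sentence. The downside is that the reported count of excess use will be higher. Recording dose-counter readings at the calls is not a substitute, because a cumulative total hides single-day peaks.

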7.4. Clinical Laboratory Tests

Any patient who experiences menarche following screening will be required to have a negative urine pregnancy test prior to dosing with IMP. If a patient has a positive urine pregnancy test, then they will be discontinued from the study. Procedures for reporting pregnancy are provided in Section [7.1.5.3](#).

7.5. Physical Examinations

Physical examinations, including height (to be obtained at the screening visit only) and weight, will be performed at the time points detailed in [Table 1](#).

A physical examination will include, at a minimum, skin, lungs, cardiovascular, respiratory, gastrointestinal, and neurological assessments. Height (to be obtained at the screening visit only) and weight will also be measured and recorded.

Investigators should pay special attention to clinical signs related to previous serious illnesses.

7.6. Vital Signs

Vital signs (blood pressure [systolic/diastolic], respiratory rate, and heart rate) will be measured at the screening visit ([Table 1](#)) for inclusion criteria assessment only and will not be used for safety assessment.

7.7. Electrocardiography

Electrocardiogram will not be measured in this study.

**8. ASSESSMENT OF PHARMACOKINETICS/
PHARMACODYNAMICS/
BIOMARKERS/PHARMACOGENOMICS/ IMMUNOGENICITY/
ANCILLARY STUDIES**

Pharmacokinetic, pharmacodynamic, biomarker, pharmacogenomics, immunogenicity, or other ancillary parameters will not be evaluated in this study.

9. STATISTICS

This section describes the statistical analysis as foreseen at the time of planning the study. Changes, additions, and further details about the analyses will be described in the statistical analysis plan. After finalization of the statistical analysis plan, any additional analyses or changes to analyses that may be required will be fully disclosed and justified in the clinical study report (CSR).

9.1. Sample Size and Power Considerations

Assuming an expected dropout rate of 10%, it is recommended that 400 patients be enrolled so that 360 evaluable patients complete the study. These conclusions are based on a review of the relevant literature, as follows.

Based on previous studies of an exacerbation-prone COPD cohort ([Dransfield et al 2013](#), [Vogelmeier et al 2011](#), [Wedzicha et al 2013](#), [Wedzicha et al 2016](#)), it is expected that 91 (range, 73 to 110) CE-COPD events will occur over the 12-week evaluation period in this study based on reported CE-COPD exacerbation rates of 1.05 and 1.14 events per year. Furthermore, it is expected that 14% (14) of total exacerbations will be severe.

This sample size (ie, n=400 patients, 73 to 110 CE-COPD events) is considered adequate for the fulfillment of the study objectives to evaluate the relationship of albuterol use, inspiratory flow, SDI, and TDS data associated with a subsequent CE-COPD event. Per a previous study ([Jenkins et al 2013](#)), a statistically significant relationship was established between daily SABA usage and subsequent CE-COPD.

In the present study, approximately 73 to 110 CE-COPD events are desired because the model's fitting of the current study involves the analysis of multiple predictors as described in more detail below. Because the largest model considered has 7 covariates, it is desirable to have at least 70 events. The probability to observe at least 70 CE-COPD events is higher than 0.99.

Risk models published in the literature have typically included between 4 and 6 covariates/risk factors ([Bateman et al 2015](#), [Greenberg et al 2012](#), [Quezada et al 2016](#)) to examine the relationship between possible risk factors and a disease. When there is more than 1 covariate (risk factor) in the model, multiple logistic regression may be used to estimate the relationship of a specific covariate of interest (ie, albuterol use) to a primary outcome (ie, CE-COPD), adjusting for the other/remaining covariates (risk factors). In this case, the required sample size to estimate such a relationship is greater than that for univariate logistic regression.

The number of events per variable has been suggested as a criterion for the size of a data set ([Harrell et al 1984](#), [Laupacis et al 1997](#), [Peduzzi et al 1996](#),). The rule of thumb when building logistic regression models is 1 predictor variable for every 10 events ([Peduzzi et al 1996](#), [Vittinghoff and McCulloch 2007](#)). Therefore, this sample size would be adequate for predicting the primary outcome (CE-COPD) using multiple logistic regression, including the covariate of primary interest (ie, albuterol use) and the remaining multiple predictors (inspiratory flow values, SDI, and TDS) as potential risk factors for CE-COPD in the model for this patient population.

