6.1.3. Inspiratory Flow Values Upon Albuterol Dosing

Inspiratory flow values will include (1) maximal inhalational flow (MIF), (2) inhalational volume, (3) inhalational duration and (4) time to MIF. The inhalational flow data will be downloaded using extraction software directly from eMDPI devices collected from the patients at their final study visit after return of the device to the depot.

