9.5.2.1. Endpoint Analysis

The relationship between albuterol usage and CE-COPD will be analyzed as follows, without controlling for multiplicity.

The multiple device-use-measures will be used as predictors of CE-COPD in the following stepwise selection logistic regression models to select significant predictors in a forward manner:

1. albuterol usage
2. albuterol usage + inspiratory flow values
3. albuterol usage + SDI
4. albuterol usage + TDS
5. albuterol usage + inspiratory flow values + SDI

6. albuterol usage + inspiratory flow values + TDS

The selection of covariates will be performed at the 0.2 level.

Demographic variables and disease state information collected at study enrollment will also be considered as predictors. Because the device-use-measures will be collected continuously over time, these measures could be used to derive many potential predictors of risk. For example, with respect to albuterol use, a subject using the inhaler 3 times in the span of a 2-day or 3-day period could be a strong predictor of a CE-COPD, but a better marker for risk might be 10 times in the span of a week. There are no prior robust data to inform these decisions; 1 possible benefit of this work will be to examine the relationship between multiple functional forms for the device-use-measures to determine which forms have predictive power.

Furthermore, the effect of including interaction terms in the model (ie, testing the assumption of additivity of predictors on the log odds scale) will also be studied. Pair-wise interactions will be assessed at the 0.01 significance level to avoid weak interaction signals that would potentially not translate when applying the risk score to new cohorts. Goodness-of-fit tests may be applied to make sure that the finally selected model fits the data closely. The C-statistic ([Hosmer et al 2013](#)) will be used to compare the goodness of fit of various logistic regression models in terms of how well the predictor(s) discriminate between patients with and without CE-COPD.

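### The 70-event target rests on 7 covariates that are never listed and do not match the plan's own largest models, so adequacy at 10 events per variable is not shown

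*Protocol*

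**What the plan says.** Protocol 9.1, the synopsis and SAP 2.3 carry the same chain of reasoning. The rule is "The rule of thumb when building logistic regression models is 1 predictor variable for every 10 events". The target follows from it: "Because the largest model considered has 7 covariates, it is desirable to have at least 70 events". The supply of events is "it is expected that 91 (range, 73 to 110) CE-COPD events will occur over the 12-week evaluation period in this study". Behind that figure stand two annual rates taken from the literature, 1.05 and 1.14 per patient, and the recommendation that "400 patients be enrolled so that 360 evaluable patients complete the study". The probability of seeing at least 70 events is put above 0.99, and the sample size is then declared adequate for multiple logistic regression.

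Protocol 9.5.2.1 lists six models. The largest are model 5 (albuterol usage, inspiratory flow values and SDI) and model 6 (the same with TDS in place of SDI). On flow, Protocol 6.1.3 says "Inspiratory flow values will include (1) maximal inhalational flow (MIF), (2) inhalational volume, (3) inhalational duration and (4) time to MIF". Protocol 9.5.1 defines SDI as one composite. Protocol 9.5.2.1 then adds "Demographic variables and disease state information collected at study enrollment will also be considered as predictors" and says of the device measures that "these measures could be used to derive many potential predictors of risk". It plans to compare several functional forms, to select covariates forward at the 0.2 level, and to test pair-wise interactions at the 0.01 level.

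Neither document lists the 7 covariates. SAP 7.5.3 and 20.4 pass the predictive modelling to a separate group and a separate report.

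**The concern.** The target is 10 times the covariate count, so it is only as good as that count. The sentence declaring adequacy names albuterol use, flow values, SDI and TDS and contains no baseline or demographic term. The analysis section says such terms will be considered. The event budget and the model-building procedure therefore describe different sets of predictors.

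The protocol gives no power calculation, so this chain is the whole quantitative case for 400 patients. If the count is too low, a reader will take a model selected from a wider set of predictors to be better supported by events than it is.

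**Working it through.** **Inputs.** From Protocol 9.1: 360 evaluable patients, 10% dropout, rates of 1.05 and 1.14 per year (midpoint 1.095), 12 weeks, 10 events per variable, 7 covariates. From Protocol 6.1.3: 4 flow values. From Protocol 9.5.1: SDI as 1 composite. From Protocol 9.5.2.1: the model list and the baseline predictors.

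**Reproducing the plan.**
- Enrolment: 360 / 0.9 = 400.
- Expected events: 360 × 1.095 × 12/52 = 90.97, that is 91.
- Poisson 2.5% and 97.5% points at that mean: 73 and 110.
- Target: 7 × 10 = 70, with P(at least 70) = 0.990.

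Every stated figure is recovered. The question is only about the 7.

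**Counting models 5 and 6.** At the leanest, take one albuterol summary, four flow values, and SDI or TDS as one term:
- Device terms: 1 + 4 + 1 = 6.
- Plus one demographic and one disease-state term: 6 + 2 = 8.
- Plus two demographic variables (the protocol uses the plural) and one disease-state term: 6 + 3 = 9.

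Protocol 6.1.2 names three albuterol parameters. If all three were entered, the device count alone would be 3 + 4 + 1 = 8, and one demographic plus one disease-state term would make 10. I do not rely on this, because one of the three (days before the peak when use rose) is defined only for patients with an event.

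**What the expected events support.** Events per term are 90.97/k. The probability of meeting the rule is the Poisson tail P(X ≥ 10k) at mean 90.97.

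| Terms k | Events needed | Events per term | P(X ≥ 10k) |
|---|---|---|---|
| 7 | 70 | 13.0 | 0.99 |
| 8 | 80 | 11.4 | 0.89 |
| 9 | 90 | 10.1 | 0.55 |
| 10 | 100 | 9.1 | 0.18 |

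Across the two rates the plan cites, the probability at 8 terms runs from 0.79 (1.05 per year, mean 87.2) to 0.94 (1.14 per year, mean 94.7). Since 91/10 = 9.1, the rule allows at most 9 terms at the expected number of events, and 7 at the plan's lower limit of 73.

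This check follows the plan in setting its largest model against the full 91 events. SDI and TDS are recorded only in subsets of 100 patients each. That is a separate matter and is not counted here.

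**The case against.** The best defence is that 7 can be reached. Models 5 and 6 with a single baseline term give 1 + 4 + 1 + 1 = 7. Model 2, which needs no accelerometer, gives 1 + 4 + 2 = 7 with one demographic and one disease-state term. The predictors named in the adequacy sentence also give 1 + 4 + 1 + 1 = 7. So a reader who infers that no count yields 7 goes too far. Each route is strained, however. The first leaves out either the demographic or the disease-state part. The second is not the largest model and needs a single demographic variable. The third puts SDI and TDS together, which no listed model does, and has no baseline term.

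A second defence is that 91 events still give 11.4 and 10.1 per variable at 8 and 9 terms, so the rule is met in expectation. That stands. A reader might infer that the sample is shown to be inadequate even with every event usable, but the documents do not support this. Failure in expectation begins at 10 terms, and the number of baseline terms is not stated. Nor should the demographic and history items in SAP 5.3 to 5.6 be added up to reach 20 or more candidates: those sections describe summaries, not model terms.

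Third, the documents apply the rule to covariates in a model and do not say that screened candidates count. That is correct as a reading. But forward selection uses the outcome data on every candidate it tests, so a budget that counts only a final model understates the demand on the events. The counts of 8 and 9 above need only predictor classes the plan says it will consider.

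Finally, the study is exploratory, the SAP prevails over the protocol, and the modelling is to be reported separately. This lowers the stakes. It does not remove the adequacy claim, which SAP 2.3 still makes.

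**Conclusion.** The point holds as a failure to support a stated claim. It is neither an arithmetic error nor proof that 400 patients are too few. The 7 is undefined, falls between the 6 device terms of the largest models and the 8 or 9 that result once baseline predictors are included, and leaves no visible room for functional forms or interactions. On the plan's own rate and rule, the probability of meeting 10 events per term drops from 0.99 to 0.89 at 8 terms and 0.55 at 9. From 10 terms the rule is not met in expectation (9.1 per term, probability 0.18).

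The calculation assumes Poisson event counts at the midpoint rate, 360 patients followed for 12 weeks, all events usable, one albuterol summary, four flow values and a composite SDI. How far beyond 9 the count goes depends on how many baseline terms and functional forms are screened, which the documents leave open.

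**What to change.** In Protocol 9.1, the synopsis and SAP 2.3, replace the 7-covariate, 70-event statement with three things: the number k of candidate terms that will be screened (device terms in every functional form tried, plus baseline variables), the resulting events per candidate (91/k), and the probability of reaching 10k events. Limit the adequacy sentence to what those figures support.

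If the sponsor prefers to keep the 70-event claim, prespecify at most 7 named candidate terms for the full-sample model and label any analysis beyond that list as hypothesis generating. If the list is to sit in the separate analytics report, SAP 7.5.3 should refer to it, and it should be fixed before database lock.

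The cost is wording. No extra patients or data are needed. The downside is a less favourable adequacy statement or, under the second option, a shorter list of predictors with prespecified status.
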